Appendix 5. Glasgow Coma Scale¹⁸

Component	Rating	Score
Eyes Open	Spontaneous	4
	To sound	3
	To pressure	2
	None	1
Verbal Response	Oriented	5
	Confused	4
	Words	3
	Sounds	2
Motor Response	None	1
	Obeys commands	6
	Localising	5
	Normal flexion	4
	Abnormal flexion	3
	Extension	2
	None	1

Appendix 6. Modified Rankin Scale (mRS)¹⁹

Score	Description
0	No symptoms at all
1	No significant disability despite symptoms; able to carry out all usual duties and activities
2	Slight disability; unable to carry out all previous activities, but able to look after own affairs without assistance
3	Moderate disability; requiring some help, but able to walk without assistance
4	Moderately severe disability; unable to walk without assistance and unable to attend to own bodily needs without assistance
5	Severe disability; bedridden, incontinent and requiring constant nursing care and attention
6	Dead

The following link should be used to access the training module for the mRS:

<https://secure.trainingcampus.net/uas/modules/trees/windex.aspx?rx=rankin-english.trainingcampus.net>

Appendix 7. Abbreviations

This is a list of abbreviations that may be used in the protocol.

Abbreviation	Term
ADA	anti-drug antibody
ADE	adaptive design explorer
AE	adverse event
AHA/ASA	American Heart Association/American Stroke Association
ALT	alanine aminotransferase
Anti-CHO	anti-Chinese hamster ovary
Anti-PACE	anti-paired basic amino acid cleaving enzyme
APC	activated protein C
aPTT	activated partial thromboplastin time
AST	aspartate aminotransferase
ATIII	antithrombin III
BID	twice daily
BP	blood pressure
CA	Competent Authority
CDS	core data sheet
CRF	case report form
CRM	continual reassessment method
CSA	clinical study agreement
CTA	clinical trial application
CTCAE	Common Terminology Criteria for Adverse Events
CT	computed tomography
CV	coefficient of variation
DNA	deoxyribonucleic acid
DU	dispensable unit
DVT	deep vein thrombosis
EC	effective concentration
EC	ethics committee
ECG	electrocardiogram
ED	effective dose
eDMC	external data monitoring committee
EDP	exposure during pregnancy
EDTA	edetic acid (ethylenediaminetetraacetic acid)
ELISAs	Enzyme-linked immunosorbent assays
EMS	emergency medical services
ESO	European Stroke Organisation
EudraCT	European Clinical Trials Database
FDA	Food and Drug Administration (United States)
FDAAA	Food and Drug Administration Amendments Act (United States)

Abbreviation	Term
FIH	first in human
FSH	follicle-stimulating hormone
FVa	factor Va
FX	factor X
GCP	good clinical practice
GCS	Glasgow coma scale
GLP	good laboratory practice
HEENT	head, eyes, ears, nose and throat
IB	investigator's brochure
ICH	intracerebral hemorrhage
ICH	International Conference on Harmonisation
ICU	intensive care unit
ID	identification
IND	investigational new drug application
INR	international normalized ratio
IRB	institutional review board
IRC	internal review committee
IRT	interactive response technology
IUD	intrauterine device
IV	intravenous
IVH	intraventricular hemorrhage
IVR	interactive voice response
IWR	interactive web response
kg	kilogram
LFT	liver function test
LMWH	low molecular-weight heparin
LRP	lipoprotein receptor-related protein
LSLV	last subject last visit
MCMC	Markov Chain Monte Carlo
mCRM	modified continual reassessment method
MED	minimum effective dose
MR or MRI	magnetic resonance imaging
mRS	modified Rankin score
MTD	maximum tolerated dose
NAb	neutralizing antibody
N/A	not applicable
NCI	National Cancer Institute
NIHSS	National Institute of Health Stroke Scale
NOAL	no observed effects level
NOAEL	no observed adverse effect level
OBU	Oncology Business Unit
PD	pharmacodynamic
PE	pulmonary embolism

Abbreviation	Term
PF1+2	prothrombin fragment 1+2
PK	pharmacokinetic
PT	prothrombin time
PWRD	Pfizer Worldwide Research and Development
RNA	ribonucleic acid
RR	respiratory rate
SAE	serious adverse event
SAP	statistical analysis plan
SCL	Supply Chain Lead
SoA	schedule of activities
SOP	standard operating procedure
SPC	summary of product characteristics
SRSD	single reference safety document
SUSAR	Suspected Unexpected Serious Adverse Reaction
TAT	thrombin-antithrombin
TEAE	treatment emergent adverse event
TIE	thromboembolic and/or ischemic event
TFPI	tissue factor pathway inhibitor
TX	toxicokinetics
VISTA	virtual international stroke trial archive
WBC	white blood cell
ULN	upper limit of normal
US	United States
USPI	United States package insert

Appendix 8. Definition for Subjects Capable of Providing Consent in Sweden

Enrollment of subjects in Sweden is limited to individuals who are able to provide their personal informed consent. Individuals conscious, oriented and able to follow commands are considered able to provide their own consent and in Sweden these individuals are operationally defined by the following criteria:

Inclusion Criteria

- Glasgow Coma Scale score ≥ 14 .

Exclusion Criteria

- Individuals with aphasia (verbal Glasgow Coma Scale score < 5 and NIH Stroke Scale Score > 0 in item 9).
- Individuals with dementia.
- Individuals with a reduced level of consciousness (NIH Stroke Scale score ≥ 1 in item 1).

## 1. VERSION HISTORY

The first version of the Statistical Analysis Plan (SAP) for study B2341002 was based on the protocol amendment 1 dated 28 June 2016. This SAP amendment reflects changes made to the protocol to ensure that the analyses described are consistent with those described in the study protocol amendment 2 dated 17 January 2017.

Pfizer made the decision to terminate the study early after 21 subjects were enrolled in the study in October 2017. Changes in the analyses plan reflect this early study termination.

**Table 1. Summary of Major Changes in SAP Amendments**

Version: SAP amendment 1	
Summary of Changes	Rationale

Removed the requirement for AEs to be in the same system organ class from the criteria for sequential dosing and ad hoc eDMC meetings.

Added cardiac troponin T results to the requirements for 72-hour safety data review. This applies only to sites where cardiac troponin T is analyzed locally.

Added a statement on the precedence of centrally-analyzed troponin I, versus locally analyzed troponin T, for safety data review purposes.

	This was required by regulatory authorities in Germany and was reflected in protocol amendment 2.
Added “based on available data during the safety review period after each respective cohort completes dosing.” Section 6.1.1.1. and minor edits on Section 7.4.2.	Clarification of the mCRM analyses and safety review procedure conducted between Cohorts.
Added a footnote to Table 4	Clarification of the extended visit window for discharge day other than Day 8.

Removed subset analyses (Section 6.4), wordings referring to Kaplan-Meier analyses, mixed effects model for repeated measures, analyses of CT parameters and exploratory efficacy endpoints NIHSS and mRS, sliding dichotomy and ordinal analyses of mRS.

Simplified graphical presentation and analyses of

	Early study termination: Limitation of sample size and the business decision of not to progress to Phase 2 efficacy study for ICH diminished the utility of the original proposed analyses.

various exploratory measures in Section 6.3 and Section 6.7.	
--	--

## 2. INTRODUCTION

This SAP provides the detailed methodology for summary and statistical analyses of the data collected in study B2341002. This document may modify the plans outlined in the protocol; however, any major modifications of the primary endpoint definition or its analysis will also be reflected in a protocol amendment.

### 2.1. Study Objectives

#### *Primary Objective:*

- *Based on the mCRM algorithm, determine the maximum tolerated dose (MTD) of PF-05230907 administered once as an IV bolus in subjects with ICH.*
- *Determine the overall safety and tolerability of PF-05230907.*

#### *Secondary Objectives:*

- *Evaluate PD effects of treatment with PF-05230907.*
- *Determine the frequency of antibody immune response to PF-05230907.*

#### *Exploratory Objectives:*

- *Assess hemostatic efficacy of PF-05230907.*
- *Characterize the PK profile of PF-05230907.*
- *Assess effect of PF-05230907 on exploratory biomarkers of PD in subjects with ICH.*
- *Assess potential measures of neuro-inflammation and/or neurologic outcomes in subjects with ICH.*
- *Assess brain imaging parameters that may be associated with efficacy or safety of treatment with PF-05230907 and/or outcomes in ICH.*
- *Determine frequency of antibody immune response against proteins from host cells used in manufacture of PF-05230907.*
- *Assess neurological outcome measures.*

- *Assess health resource utilization.*

## 2.2. Study Design

*This is a Phase 1b, multi-center, open-label study to determine the maximum tolerated dose (MTD) and assess the safety and tolerability, and PD of PF-05230907 administered once as an IV bolus in subjects with ICH. A modified continual reassessment method (mCRM) design based on the endpoints of treatment emergent thromboembolic and/or ischemic events (TIEs) will be adopted. The mCRM design utilizes Bayesian methodology to continuously learn the dose-toxicity relationship, which is characterized by a parametric model. The starting dose will be 5 µg/kg based on the highest dose safely administered in the first in human (FIH) clinical study (B2341001). As safeguards for subject safety, dose escalation will be conducted in a limited number of subjects per cohort (N=3). Sequential dosing criteria will be assessed for each cohort, dosing will be paused following completion of each cohort, internal safety monitoring and external Data Monitoring Committee (eDMC) review of the safety data will be conducted. The total length of time planned for study participation is approximately 3 months; 6.0 hours for screening, a single dose administration with a 4 day minimum hospital confinement period and follow-up visits through Day 91.*

The determination of MTD using mCRM dose-toxicity modeling will be based on TIEs which occur through 7 days post-dose (Day 8). *A target 15% TIE rate at the MTD will be employed for the MTD determination. The range of doses that may be explored will be from a grid of doses ranging from 1 µg/kg to 47 µg/kg. Subjects will be enrolled in cohorts of 3, starting with an initial dose of 5 µg/kg for the first cohort. If the modeled rate of TIEs at the 5 µg/kg starting dose exceeds the pre-specified target toxicity rate of 15% for the MTD, lower doses may be explored. Starting with the second cohort, subjects will be assigned to a dose in the pre-defined dose grid that is closest to, but not exceeding, the currently predicted MTD based on a parametric dose-toxicity model that the mCRM utilizes to learn about the overall dose-TIE relationship subject to additional dose escalation constraints and clinical oversight. The dose-toxicity model is updated based on the frequency of TIEs in each completed cohort. Under the adopted mCRM design, the dose level for each subsequent cohort can be escalated, deescalated, or restudied but always aiming towards the MTD target based on the frequency of TIEs.*

To avoid an overly aggressive dose escalation scheme (especially early in the trial when limited TIE data is available), the maximum allowed dose increase from the highest dose that has been previously studied is limited to 2 increments at a time (ie, not more than one dose level may be skipped ([Table 2](#)), which results in a 50-67% increase in dose from the 5 µg/kg dose. Four doses (1-4 µg/kg) lower than the starting dose are included in the dose grid to allow dose de-escalation if a high TIE rate occurs in the first cohort assigned to 5 µg/kg. In addition, Pfizer might modify the dose level assignment for the next cohort from the model-based estimate to a more conservative dose level based upon clinical oversight or external Data Monitoring Committee (eDMC) recommendations.

**Table 2. Dose Escalation Schema**

Dose (μg/kg)	Increment from prior dose	
	Escalation = increment of 1 dose level	Escalation = increment of 2 dose level (skipped dose)
1		
2	100%	
3	50%	200%
4	33%	100%
5*	25%	67%
6	20%	50%
8	33%	60%
10	25%	67%
12	20%	50%
15	25%	50%
19	27%	58%
24	26%	60%
30	25%	58%
37	23%	54%
47	27%	57%

\* The starting dose is 5 μg/kg. If the TIE rate at the starting dose exceeds the pre-specified limit for the MTD, lower doses in the dose grid may be explored.

### 2.2.1. Sample Size

*No formal sample size calculation is performed.* The minimum and maximum sample sizes of the study are 20 and 51, respectively. For a cohort size of 3, the maximum study sample size is set as 51 (17 cohorts) in order to have a reasonable chance to identify the correct MTD based on statistical simulations. *The actual sample size of the study will depend on the underlying dose-TIE relationship and variability in the actual data realization. If the study stops with a MTD declared and the maximum sample size has not been reached, 12 subjects must have been studied at the MTD dose.* The number of subjects treated at each dose and a particular dose-assignment sequence cannot be pre-specified in advance due to the dynamic nature of the Bayesian allocation procedure, and not every dose listed will be actually studied.

### 2.2.2. Enrollment Pause

As safeguards for subject safety, an enrollment pause can occur within a cohort of 3 subjects, and will occur after each cohort completes dosing.

#### 2.2.2.1. Sequential dosing

Sequential dosing of subjects in a cohort meeting one of the following criteria will be implemented:

1. The initial cohort evaluating a dose level that exceeds previously administered dose levels.
2. The subsequent (second) cohort evaluating the respective dose level at which a Suspected Unexpected Serious Adverse Reaction (SUSAR) or 2 or more grade 3 or higher adverse events that are considered at least possibly related to treatment with PF-05230907 are observed in the initial cohort evaluating a dose level that exceeds previously investigated dose levels.

*An enrollment pause will be implemented following dosing of each subject in the cohort to allow for medical monitor safety data review prior to dosing the next subject. For the safety review that will take place during the enrollment pause, clinical observation results collected on the respective subject during the initial 72-hour period following dosing (treatment emergent adverse events [TEAEs], SAEs, vital sign changes, electrocardiogram [ECG] changes, Brain imaging study [CT ± MRI] scan, Doppler ultrasound of the lower extremity and cardiac troponin I [and cardiac troponin T, where applicable]) will be reviewed by the medical monitor. Other available laboratory test results at the time of this safety review will also be assessed.*

#### **2.2.2.2. Progression to subsequent cohort**

An enrollment pause will occur after each respective cohort completes dosing. Progression to each subsequent cohort of study subjects will not occur until the following are completed:

1. Sponsor review of the available safety data through Day 8 (or discharge) post-dose administration.
2. Discussion with the investigator(s)/sub-investigator(s) for each subject in the respective cohort.
3. An interim review memo including all specified 7-day safety data has been provided to the eDMC chair (or designee).
4. The mCRM-determined dose recommendation and any adjustment of mCRM-determined dose to more conservative dose levels when deemed appropriate by the sponsor or eDMC is attained.
5. An authorization has been received from the eDMC chair to proceed with enrollment of the subsequent cohort.

#### **2.2.2.3. eDMC Review of Cohort Safety Data**

*The eDMC will be responsible for ongoing cumulative reviews of the study safety data. If there is a safety concern after safety data review, at the discretion of the eDMC chair (or*

designee), the eDMC may direct that dosing at the respective dose level (or higher dose levels) be paused until a full meeting of the eDMC has been convened.

*If a Suspected Unexpected Serious Adverse Reaction (SUSAR) or 2 or more grade 3 or higher adverse events that are considered at least possibly related to treatment with PF-05230907 are observed in the initial cohort evaluating a dose level that exceeds previously investigated dose levels, then dosing at the respective dose level (and at higher dose levels) will be paused until a meeting of the eDMC has been convened. The recommendations made by the eDMC to alter the conduct of the study will be forwarded to Pfizer for final decision.*

### 2.2.3. Safety Biomarker Criteria for Dose Escalation Adjustment

To prevent overly aggressive dose-escalation, the maximum allowed dose increase from the highest dose that has been previously studied is limited to 2 increments at a time leading to a maximum of 67% increase in dose for the 5 µg/kg dose and above. This feature is incorporated into the study design module of the mCRM algorithm for dose recommendation.

Dose increase will be limited to only one increment at a time if treatment emergent modulation of one or more of the following laboratory safety biomarkers is observed during the interval from baseline to Day 4 (or discharge):

Safety Biomarker	Baseline value	Any post-dose value observed from baseline to Day 4 (or discharge)
Fibrinogen	within [LLN, ULN]	≤50% of LLN
	< LLN	≤50% of the baseline value
Platelet Count	within [LLN, ULN]	<100,000
	< LLN	≤50% of the baseline value
Prothrombin Time	No restriction	> 4 seconds above the baseline value

LLN: lower limit of normal reference range; ULN: upper limit of normal reference range

In addition to TIEs and available safety biomarker data, other available safety data including clinically significant AEs or SAEs will also be assessed. These events will not have any impact on mCRM-determined dose recommendations but may be used to inform dose assignments more conservative than those derived by the mCRM dose-toxicity model.

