The range of doses that may be explored will be from a grid of doses ranging from 1 $\mu\text{g}/\text{kg}$ to 47 $\mu\text{g}/\text{kg}$. If the modeled rate of TIEs at the 5 $\mu\text{g}/\text{kg}$ starting dose exceeds the pre-specified target toxicity rate of 15% for the MTD, lower doses may be explored. Starting with the second cohort, subjects will be assigned to a dose in the predefined dose grid that is closest to, but not exceeding, the currently predicted MTD based on a parametric dose-toxicity model that the mCRM utilizes to learn about the overall dose-TIE relationship subject to additional dose escalation constraints and clinical oversights. The dose-toxicity model is updated based on the frequency of TIEs in each completed cohort. Under the adopted mCRM design, the dose level for each subsequent cohort can be escalated, deescalated, or restudied but always aiming towards the MTD target for frequency of TIEs. However, dose level assignments may be modified to more conservative dose levels based upon sponsor medical judgment or eDMC recommendations. To prevent overly aggressive dose-escalation, the maximum allowed dose increase from the highest dose that has been previously studied is limited to 2 increments at a time (ie, not more than one dose level may be skipped) which results in 50-67% increase in dose for the 5 $\mu\text{g}/\text{kg}$ dose and above. If treatment emergent modulation of one or more of the following laboratory safety biomarkers is observed during the interval from baseline to Day 4 (or discharge), as indicated below, dose increase will be limited to only 1 increment at a time (ie, no more dose skipping):

- Fibrinogen:
 - If baseline value is within normal reference range: a post-dose value $\leq 50\%$ of the lower limit of normal.
 - If baseline value $<$ lower limit of normal reference range: a post-dose value $\leq 50\%$ of the baseline value.
- Platelet Count:
 - If baseline value is within normal reference range: a post-dose value of $< 100,000$.
 - If baseline value $<$ lower limit of normal reference range: a post-dose value $\leq 50\%$ of the baseline value.
- PT: a post-dose value that is prolonged by > 4 seconds above the baseline value.

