3.2. Progression to Subsequent Cohort

A target 15% TIE rate at the MTD will be employed for the MTD determination. The range of doses that may be explored will be from a grid of doses ranging from 1 $\mu\text{g}/\text{kg}$ to 47 $\mu\text{g}/\text{kg}$ ([Table 2](#)). Subjects will be enrolled in cohorts, starting with an initial dose of 5 $\mu\text{g}/\text{kg}$ for the first cohort (the highest dose safely administered in the first in human clinical study [B2341001]). If the modeled rate of TIEs at the 5 $\mu\text{g}/\text{kg}$ starting dose exceeds the pre-specified target toxicity rate of 15% for the MTD, lower doses may be explored. Starting with the second cohort, subjects will be assigned to a dose in the pre-defined dose grid that is closest to, but not exceeding, the currently predicted MTD based on a parametric dose-toxicity model that the mCRM utilizes to learn about the overall dose-TIE relationship subject to additional dose escalation constraints and clinical oversight. The dose-toxicity model is updated based on the frequency of TIEs in each completed cohort. Under the adopted mCRM design, the dose level for each subsequent cohort can be escalated, deescalated, or restudied but always aiming towards the MTD target based on the frequency of TIEs. However, dose level assignments may be modified to more conservative dose levels based upon sponsor medical judgment or eDMC recommendations. To prevent overly aggressive dose-escalation, the maximum allowed dose increase from the highest dose that has been previously studied is limited to 2 increments at a time (ie, not more than one dose level may be skipped-see ([Table 2](#)), which results in 50-67% increase in dose from the 5 $\mu\text{g}/\text{kg}$ dose and above. If treatment emergent modulation of one or more of the following laboratory safety biomarkers is observed during the interval from baseline to Day 4 (where available), as indicated below, dose increase will be limited to only 1 increment at a time (ie, no more dose skipping):

- Fibrinogen:
 - If baseline value is within normal reference range: a post-dose value $\leq 50\%$ of the lower limit of normal.
 - If baseline value $<$ lower limit of normal reference range: a post-dose value $\leq 50\%$ of the baseline value.
- Platelet Count:
 - If baseline value is within normal reference range: a post-dose value of $< 100,000$.

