### 5.2.3. Allocation Rule

The allocation rule is designed to consistently pick the dose with TIE rate closest to but not exceeding the target 15%, therefore maximizing the number of subjects treated at or near that

dose. This is achieved by an adaptive allocation using the model-based estimate of TIE rate at each dose.

After the TIE data from the first cohort (5  $\mu\text{g/kg}$ ) becomes available, the prior distribution of  $\beta$  will be updated into a posterior distribution through Bayesian Markov Chain Monte Carlo (MCMC) simulations in Adaptive Design Explorer (ADE). The model-based MTD will be estimated as  $f^{-1}(0.15, \hat{\beta})$ , where 0.15 is the pre-specified target TIE rate at MTD and  $\hat{\beta}$  is the posterior mean of  $\beta$ . All subjects in the next cohort will be dosed at the dose level ( $d_j^*$ ) closest to this estimated MTD but not exceeding it, ie.

$$x_j^* = \max_j [x_j : x_j < f^{-1}(0.15; \hat{\beta})]$$
$$d_j^* \leftrightarrow x_j^*$$

If the current MTD estimate is above the highest dose so far tested, this allocation rule is subject to restriction of maximum 2 dose increments, as specified in Table 2. This restriction is built in the mCRM design module for dose recommendation.

As described in Section 2.2, extensive safeguards and monitoring for subject safety will be implemented. If treatment emergent modulation of one or more of the safety biomarkers fibrinogen, platelet count, and prothrombin time is observed that exceeds pre-specified thresholds during the interval from baseline to Day 4, dose increase will be limited to only one increment at a time. Other available safety data including clinically significant AEs or SAEs will also be assessed. *These events will not have any impact on mCRM-determined dose recommendations but may be used to inform dose assignments more conservative than those derived by the mCRM dose-toxicity model.*

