### **6.6.2. Laboratory Data**

The assessment on the laboratory parameters will take into account whether each subject's baseline test result is within or outside the laboratory reference range for the particular laboratory parameter. Laboratory results for some parameters may be classified according to the CTCAE criteria version 4.03. Laboratory results that are not part of CTCAE will be presented according to the categories: below normal limit, within normal limits and above normal limit. In addition, the summary tables and data listings for the subjects who meet the criteria for potentially clinically significant abnormalities in Appendix 2, will be presented. All investigators' comments on the safety data will be listed and reviewed.

Incidence and magnitude of treatment emergent abnormal findings in the laboratory safety parameters will be summarized descriptively by dose group.

As described in Section 2.2.3, dose increase will be limited to only one increment at a time if treatment emergent modulation of fibrinogen, platelet count, or prothrombin time in excess of pre-specified thresholds is observed during the interval from baseline to Day 4 (or discharge). Listing of subjects who meet the safety biomarker criteria for dose escalation adjustment will be generated by dose group.

For Tissue Factor Pathway Inhibitor (TFPI), baseline values will be summarized descriptively. For available Prothrombin G20210A Mutation and Factor V Leiden Mutation, the number and percentage of subjects with the mutation will be summarized overall and by dose group.

For Prothrombin Time/International Normalized Ration (PT/INR), Anti-thrombin III (ATIII), D-dimer, Protein S level, Protein C activity, and cardiac Troponin I, actual values will be summarized descriptively. For safety analyses the central laboratory results for cardiac troponin I will take precedence over local determinations for cardiac troponin T.

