##### **7.4.2. Safety Review between Cohorts**

Safety data through Day 7 post-dose (Day 8) comprised of the following information will be reviewed by the medical monitor and eDMC Chair. The information include summary of significant findings in treatment emergent adverse events (TEAEs), SAEs, vital sign changes, ECG changes, brain imaging study (CT±MRI) scan, Doppler ultrasound of the lower extremity, fibrinogen, platelet count, PT, and cardiac troponin I (and cardiac troponin T where applicable) of the respective cohort and all data available by dose group. Other available laboratory test results at the time of this safety review will also be assessed.

Summary and listings of available PK and PD data will be provided to help assess where clinical exposure is relative to the No Observed Adverse Effect Level (NOAEL) and assess benefit risk. However, this is not a safety data review requirement to proceed to the next cohort. Refer to Section 2.2.2.3 for details of the eDMC review of cohort safety data, and Section 2.2.2.2 for all requirements needed to proceed to the subsequent cohort.

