## Appendix 2. Criteria for safety values of potential clinically significant abnormal results

Category/Test	Abnormal values of potential clinical significance for review
Hematology	
Hemoglobin	<0.8 times LLN
Hematocrit	<0.8 times LLN
RBC Count	<0.8 times LLN
MCV	<0.9 times LLN or >1.1 times ULN
MCH	<0.9 times LLN or >1.1 times ULN
MCHC	<0.9 times LLN or >1.1 times ULN
Platelets	<0.5 times LLN or >1.75 times ULN
Leukocytes	<0.6 times LLN or >1.5 times ULN
Total Neutrophils (Abs)	<0.8 times LLN or >1.2 times ULN
Eosinophils (Abs)	>1.2 times ULN
Basophils (Abs)	>1.2 times ULN
Lymphocytes (Abs)	<0.8 times LLN or >1.2 times ULN
Monocytes (Abs)	>1.2 times ULN
Chemistry	
Total bilirubin	>1.5 times ULN
Direct bilirubin	>1.5 times ULN
Indirect bilirubin	>1.5 times ULN
AST	>3 times ULN
ALT	>3 times ULN
Alk Phosphatase	>3 times ULN
Creatinine	>1.3 times ULN
BUN	>1.3 times ULN
Uric acid	>1.2 times ULN
Sodium	<0.95 times LLN or >1.05 times ULN
Potassium	<0.9 times LLN or >1.1 times ULN
Chloride	<0.9 times LLN or >1.1 times ULN
Bicarbonate	<0.9 times LLN or >1.1 times ULN
Calcium	<0.9 times LLN or >1.1 times ULN
Albumin	<0.8 times LLN or >1.2 times ULN
Total protein	<0.8 times LLN or >1.2 times ULN
Creatine Kinase	>2.0 times ULN

Category/Test	Abnormal values of potential clinical significance for review
Miscellaneous Laboratory Data	
D-dimer	>ULN
Prothrombin G20210A Mutation	Present
Factor V Leiden Mutation	Present
PT	Prolongation by >4 seconds above baseline
INR	$\geq 1.5$
Fibrinogen	$\leq 0.5$ times LLN when baseline is within normal range $\leq 0.5$ times baseline when baseline <LLN
Anti-Thrombin III (ATIII)	<LLN and $\geq 20\%$ decrease from baseline
Protein C activity	<LLN
Protein S level	<LLN
Cardiac Troponin I	>ULN
Urinalysis	
Urine WBC	$\geq 20/\text{HPF}$
Urine RBC	$\geq 20/\text{HPF}$
Urobilinogen	$\geq 1$
Urine Bilirubin	$\geq 1$
Vital Signs	
Pulse Rate	Supine: <40 or >120 bpm
Blood Pressure	Systolic <90 mm Hg or $\geq 30$ mm Hg change from baseline Diastolic <50 mm Hg or $\geq 20$ mm Hg change from baseline
Electrocardiogram	
PR interval	$\geq 300$ msec; $\geq 25\%$ increase when baseline >200 msec Increase $\geq 50\%$ when baseline $\leq 200$ msec
QRS interval	$\geq 140$ msec; $\geq 50\%$ increase from baseline
QTc interval	$\geq 500$ msec

Note:

LLN: lower limit of normal reference range

ULN: upper limit of normal reference range

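### A subject whose baseline fibrinogen or platelet count is above ULN can never meet that marker's criterion for limiting escalation to one increment

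*SAP*

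**What the plan says.** SAP Section 2.2.3 tabulates three safety biomarkers. For fibrinogen and platelets the threshold depends on baseline, and the first row for each applies when baseline is "within [LLN, ULN" (a closed interval, with ULN defined under the table). There the trigger is fibrinogen at or below 50% of LLN, or platelets below 100,000. The second row applies when baseline is below LLN, and the trigger is a value at or below 50% of baseline. Prothrombin time has no baseline restriction. If any criterion is met between baseline and Day 4 (or discharge), the dose increase is limited to one increment instead of two.

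The protocol uses the same two groups. The Protocol Summary has "If baseline value is within normal reference range: a post-dose value" for fibrinogen, and Protocol Section 3.2 has "If baseline value is within normal reference range: a post-dose value of" for platelets; each is followed only by a below-LLN case.

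SAP Section 5.2.3 adds no third group. It refers to "one or more of the safety biomarkers fibrinogen, platelet count, and prothrombin time is observed that exceeds pre-specified thresholds". SAP Appendix 2 repeats the split for its fibrinogen flag ("times LLN when baseline is within normal range", then below LLN), while its platelet flag has no baseline condition. SAP Section 6.6.2 plans this output: "Listing of subjects who meet the safety biomarker criteria for dose escalation adjustment will be generated by dose group".

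**The concern.** A baseline above ULN falls in neither group, so for that subject and that marker the criterion has no threshold. A larger fall ending at the same post-dose value then escapes a limit that a smaller fall would trigger. No rationale is given. No eligibility criterion specifically excludes a high fibrinogen or platelet count, whereas known thrombocytopenia is excluded.

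The limit is one of the safeguards listed in the Protocol Summary and Protocol Section 3, and it is worded as mandatory. Where it cannot operate, a smaller step depends on another marker, another cohort member, or the discretionary route in SAP Section 2.2.2.2: "adjustment of mCRM-determined dose to more conservative dose levels when deemed appropriate by the sponsor or eDMC". At stake is the size of the next dose step while the trial is escalating and, at reporting, whether the Section 6.6.2 listing and the Appendix 2 fibrinogen flag are complete.

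**Working it through.** **1. Dose steps.** From the Table 2 grid, from 5 µg/kg upward, two-level steps run from 50% (8 to 12) to 66.7% (6 to 10). This reproduces the stated maximum of 67%. One-level steps run from 20% (5 to 6) to 33.3% (6 to 8).

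**2. The criterion as written.** The documents give no reference ranges, so assume fibrinogen 2.0–4.0 g/L and platelets 150–400 ×10⁹/L.

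- Fibrinogen baseline 4.0 (equal to ULN) triggers at a post-dose value of 1.0 or less. Baselines of 4.01, 5 and 6 never trigger, even at 0.
- Platelet baseline 400 triggers below 100. Baselines of 401 and 500 never trigger, even at 0.
- A fibrinogen fall from 3.9 to 0.95 (75.6%) triggers. A fall from 4.2 to 0.95 (77.4%) does not.

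The result above ULN does not depend on the assumed ranges.

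**3. When the cap sets the dose.** Inputs are the Unif[0,3] prior on β and the Table 3 rates p at β = 1, so the modeled rate is p^β. The posterior mean of β is plugged in, and the recommendation is the highest dose with a modeled rate below 15%.

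| TIE data | Posterior mean β | Model dose (µg/kg) | Next dose, two-level cap | Next dose, one-level limit |
|---|---|---|---|---|
| 0/3 at 5 | 1.82 | 19 | 8 | 6 |
| 0/3 at 5 and 8 | 1.97 | 24 | 12 | 10 |
| 0/3 at 5, 8 and 12 | 2.11 | 24 | 19 | 15 |
| 1/3 at 5 | 0.72 | 4 | 4 | 4 |
| 0/3 at 5, 1/3 at 8 | 1.13 | 10 | 10 | 10 |
| 0/3 at 5 and 8, 1/3 at 12 | 1.52 | 15 | 15 | 15 |

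The rounded x values of Table 3 give the same doses in all six rows. In the first three rows the cap, not the model, sets the dose. In the last three the gap changes nothing.

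**4. Chance of a TIE-free first cohort.** At the 5–10% background rate in Protocol Section 1.4, 0.95³ = 0.857 and 0.90³ = 0.729, so 73–86%.

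**5. Where animal data show fibrinogen falls.** Protocol Section 1.3.1.2 reports marked decreases in monkeys given 0.1 to 0.5 mg/kg/day. Assuming 0.1 mg/kg/day was given BID and PK is linear, each dose is 0.05 mg/kg, twice the NOAEL dose of 0.025. Cmax is then 2 × 229 = 458 ng/mL and AUC 2 × 22.9 = 45.8 ng·h/mL. Protocol Table 1 predicts 341.36 and 40.34 at 37 µg/kg, and 433.62 and 51.25 at 47 µg/kg. That is the top of the human grid.

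**6. Number of subjects.** The share with a baseline above ULN is not given. An assumed 2–20% of 21 subjects is 0.4–4.2 subjects. This counts high baselines, not missed triggers.

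**The case against.** The strongest objection is about importance. The steps most affected start from 5, 8 and 12 µg/kg, where predicted Cmax is 5.0-, 3.1- and 2.1-fold below the monkey NOAEL value, and the first-in-human study saw no clinically significant fibrinogen or platelet changes up to 5 µg/kg. At the higher doses, where such falls are more plausible, the model leaves less room. After 0/3 at 5, 8, 12 and 19, β is 2.25 and the model dose is 30 from the Table 3 rates but 24 from the rounded x values, so whether the gap matters there depends on rounding. After a further 0/3 at 30, β is 2.38 and the dose stays at 30. Reaching 19 and completing it without a TIE has probability 0.90¹² to 0.95¹², or 28–54%, at background rates. Platelet support is weaker still: marked falls are reported at 3 mg/kg/day and above, 60 times the 0.05 mg/kg/day NOAEL.

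Other controls remain. The between-cohort review in SAP Section 7.4.2 covers "fibrinogen, platelet count, PT, and cardiac troponin I", and no cohort opens without the eDMC chair's authorization. PT can trigger from any baseline. Grade 3 or higher DIC counts as a TIE. A missed trigger still leaves the two-level cap in place.

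All of this stands and keeps the point minor. It does not show that the criterion can be met above ULN. Review with discretion to lower the dose is also not the automatic limit that the plan promises.

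**Conclusion.** The concern holds. In the SAP and in both protocol statements of the rule, the fibrinogen or platelet criterion cannot be met by a subject whose baseline for that marker is above ULN. This follows from the text alone. The gap is per marker: PT, the other marker or another cohort member can still trigger the limit.

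Its possible effect is one grid level in the next dose, such as 8 instead of 6 µg/kg, and only when the model recommends at least two levels up. How often a qualifying fall would follow a high baseline is unknown. The reference ranges and the 2–20% share are assumptions, and the exposure comparison assumes BID dosing and linear PK.

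With enrollment ended at 21 subjects, the remaining effect is on reporting. Such falls would still appear in the general summaries of treatment-emergent laboratory abnormalities. Only the Section 6.6.2 listing and the Appendix 2 fibrinogen flag could omit them. This is worth correcting but is not a serious fault.

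**What to change.** **For this terminated study:** keep SAP Section 2.2.3 unchanged as the record of the rule that governed dosing. Widen the within-range condition in the Appendix 2 fibrinogen row to baseline at or above LLN. In the Section 6.6.2 listing, separately flag subjects with a baseline above ULN who meet the widened threshold (fibrinogen at or below 50% of LLN, or platelets below 100,000). The cost is one table cell and one flag.

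**For a running trial or any reuse:** in the Protocol Summary, Protocol Section 3.2 and SAP Section 2.2.3 together, replace the within-range condition with baseline at or above LLN for both markers, keeping the thresholds. The cost is wording edits in two protocol sections and one SAP table, and occasionally a smaller escalation step.

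Nothing changes for baselines at or below ULN, and over-triggering is unlikely. From a baseline above ULN, the fall must exceed:

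- **Fibrinogen:** 1 − 0.5 × LLN/ULN, which is 75.0% (2.0–4.0 g/L), 78.6% (1.5–3.5) or 80.0% (1.8–4.5).
- **Platelets:** 1 − 100/ULN, which is 73.0%, 75.0% or 77.8% for an assumed ULN of 370, 400 or 450 ×10⁹/L.
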